## 10.10 Return of individual research results.

In this section, provide your plans for the return of individual results. An “individual research result” is any information collected, generated or discovered in the course of a research study that is linked to the identity of a research participant. These may be results from screening procedures, results that are actively sought for purposes of the study, results that are discovered unintentionally, or after analysis of the collected data and/or results has been completed.

See the [GUIDANCE Return of Individual Results](#) for information about results that should and should not be returned, validity of results, the Clinical Laboratory Improvement Amendment (CLIA), consent requirements and communicating results.

**a. Is it anticipated that the research will produce any individual research results that are clinically actionable?**

“Clinically actionable” means that there are established therapeutic or preventive interventions or other available actions that have the potential to change the clinical course of the disease/condition, or lead to an improved health outcome.

In general, every effort should be made to offer results that are clinically actionable, valid and pose life-threatening or severe health consequences if not treated or addressed quickly. Other clinically actionable results should be offered if this can be accomplished without compromising the research.

	No
	Yes

→ If yes, answer the following questions (a.1-a.3).

**a.1. Describe the clinically actionable results that are anticipated and explain which results, if any, could be urgent (i.e. because they pose life-threatening or severe health consequences if not treated or addressed quickly).**

Examples of urgent results include very high calcium levels, highly elevated liver function test results, positive results for reportable STDs.

Research assessments include measures of depression which may indicate depression which will need treatment. We will inform subjects who score above the clinical cut off the results of their questionnaire and advise them to share these results with their primary care provider and seek treatment for depression. For all subjects, whether they score above the cut off or not, anyone who scores anything other than 0 on the 9th question of the PHQ-9 will be informed of this and will receive further assessment / intervention as outlined in the attached suicidality protocol.

**a.2. Explain which of these results will be offered to subjects.**

Depression scores  
Suicidal ideation / thoughts of self-harm

**a.3. Explain which results will not be offered to subjects and provide the rationale for not offering these results.**

Reasons not to offer the results might include:

- There are serious questions regarding validity or reliability
- Returning the results has the potential to cause bias
- There are insufficient resources to communicate the results effectively and appropriately
- Knowledge of the result could cause psychosocial harm to subjects

N/A

**b. What is the plan (if any) for offering subjects any results that are not clinically actionable?**

Examples: non-actionable genetic results, clinical tests in the normal range, experimental and/or uncertain results.

	No
	Yes

Document Date & Version

11/15/2019

Version 2.2

#2003

Researcher Date & Version

mm/dd/yyyy

Version x.x

Page 47 of 51

→ If yes, explain which results will be offered to subjects and provide the rationale for offering these results.

c. Describe the validity and reliability of any results that will be offered to subjects.

*The IRB will consider evidence of validity such as studies demonstrating diagnostic, prognostic, or predictive value, use of confirmatory testing, and quality management systems.*

N/A

d. Describe the process for communicating results to subjects and facilitating understanding of the results. In the description, include who will approach the participant with regard to the offer of results, who will communicate the result (if different), the circumstances, timing, and communication methods that will be used.

N/A

e. Describe any plans to share results with family members (e.g. in the event a subject becomes incapacitated or deceased).

N/A

f. Check the box to indicate that any plans for return of individual research results have been described in the consent document. If there are no plans to provide results to participants, this should be stated in the consent form.

See the [GUIDANCE Return of Individual Results](#) for information about consent requirements.

Confirmed

**10.11 Commercial products or patents.** Is it possible that a commercial product or patent could result from this study?

No  
 Yes

→ If yes, describe whether subjects might receive any remuneration/compensation and, if yes, how the amount will be determined.

N/A

## 11 ECONOMIC BURDEN TO PARTICIPANTS

**11.1 Financial responsibility for research-related injuries.** Answer this question only if the lead researcher is not a UW student, staff member, or faculty member whose primary paid appointment is at the UW.

For each institution involved in conducting the research: Describe who will be financially responsible for research-related injuries experienced by subjects, and any limitations. Describe the process (if any) by which participants may obtain treatment/compensation.

**11.2 Costs to subjects.** Describe any research-related costs for which subjects and/or their health insurance may be responsible (examples might include: CT scan required for research eligibility screening; co-pays; surgical costs when a subject is randomized to a specific procedure; cost of a device; travel and parking expenses that will not be reimbursed).

N/A

**11.3 Reimbursement for costs.** Describe any costs to subjects that will be reimbursed (such as travel expenses).

N/A

## 12 RESOURCES

**12.1 Faculty Advisor.** (For researchers who are students, fellows, or post-docs.) Provide the following information about the faculty advisor.

- Advisor's name
- Your relationship with your advisor (for example: graduate advisor; course instructor)
- Your plans for communication/consultation with your advisor about progress, problems, and changes.

N/A

**12.2 UW Principal Investigator Qualifications.** Upload a current or recent Curriculum Vitae (CV), Biosketch (as provided to federal funding agencies), or similar document to the Local Site Documents page in Zipline. The purpose of this is to address the PI's qualifications to conduct the proposed research (education, experience, training, certifications, etc.).

For help with creating a CV, see [http://adai.uw.edu/grants/nsf\\_biosketch\\_template.pdf](http://adai.uw.edu/grants/nsf_biosketch_template.pdf) and <https://education.uwmedicine.org/student-affairs/career-advising/year-4/residency-applications/curriculum-vitae/>

The CV will be uploaded.

**12.3 UW Study team qualifications.** Describe the qualifications and/or training for each UW study team member to fulfill their role on the study and perform study procedures. (You may be asked about non-UW study team members during the review; they should not be described here.) You may list these individuals by name, however if you list an individual by name, you will need to modify this application if that individual is replaced. Alternatively, you can describe study roles and the qualifications and training the PI or study leadership will require for any individual who might fill that role. The IRB will use this information to assess whether risks to subjects are minimized because study activities are being conducted by properly qualified and trained individuals.

**Describe: The role (or name of person), the study activities they will perform, and the qualifications or training that are relevant to performing those study activities.**

**There is no study team.**

All study team members will have copies of the current UW IRB procedures and requirements. They will follow these guidelines in their related duties and functions.

## 13 OTHER APPROVALS, PERMISSIONS, and REGULATORY ISSUES

**13.1 Approvals and permissions.** Identify any other approvals or permissions that will be obtained. For example: from a school, external site/organization, funding agency, employee union, UW Medicine clinical unit.

*Do not attach the approvals and permissions unless requested by the IRB.*

Institutional Ethics Committee (IEC), St.John's Medical College & Hospital, St.John's National Academy of Health Sciences, [name]

**13.2 Financial Conflict of Interest.** Does any UW member of the team have ownership or other Significant Financial Interest (SFI) with this research as defined by [UW policy GIM 10](#)?

**No**

**Yes** → If yes, has the Office of Research made a determination regarding this SFI as it pertains to the proposed research?

**No** → If no, contact the Office of Research [contact], [[contact]](mailto:[contact])) for guidance on how to obtain the determination

**Yes** → If yes, upload the Conflict Management Plan for every UW team member who has a FCOI with respect to the research, to **Zipline**. If it is not yet available, use the text box to describe whether the Significant Financial Interest has been disclosed already to the UW Office of Research and include the FIDS Disclosure ID if available.

**Statistical Methods:**

Assumptions of normality was assessed using Q-Q plot. Descriptive statistics, mean and standard deviation for normally distributed variables were used to describe the outcome parameters PHQ, QIDS. WHODAS and BADS. Chi-square test or Fisher's exact tests as appropriate, was used to test the association between baseline characteristics between study groups. At each time of assessment, outcome parameters were compared between study groups using independent t test or Mann Whitney U test as appropriate. Change in the outcome at 3 and 6 months from baseline was compared between the study groups using Wilcoxon signed rank test. McNemar Chi-square test was used to compare the change in the proportion of depression categories from baseline within each study group. In addition, RMANOVA was performed to compare the change in the outcome scores over time between study groups. A p-value of  $< 0.05$  was considered statistically significant. All analyses were performed using SPSS version 26.0.

---

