**Background:** Undiagnosed and untreated depression is a significant cause of morbidity and mortality in low-middle-income countries (LMIC) such as India. The rates of diagnosis and treatment of depression among women in rural India are disproportionately low despite a primary care based task-sharing model of mental-health treatment. Stepped care approaches support appropriate treatment of symptoms while reducing the burden on healthcare systems and mobile technology can reduce the mental health treatment gap given its reach and easy access. However, as our preliminary study at a task-sharing care model in rural south India (Maanasi clinic, situated 60 miles from Bangalore city) revealed: illiteracy and the practice of sharing mobile phones as a family resource present hurdles to the adoption of mobile mental health (mHealth) based interventions. *To date, the feasibility of an mHealth application to screen depression, track symptom severity and support the delivery of stepped care treatment has not been tested in LMIC.*

**Specific Aim 1:** In phase I of this exploratory study, we will adopt a user centered participatory approach to design and develop a multiple-user, voice-response, mobile application (“MITHRA”), to be used in community-based organizations for screening, tracking and supporting stepped care treatment for depression, including select modules of the Healthy Activity Program, a brief psychological intervention based on behavioral activation. The application will include audio, video and enhanced touchscreen capabilities, to overcome the barrier of illiteracy and lack of access.

**Specific Aim 2:** In phase II, using a randomized-control design, we will examine feasibility and utility of “MITHRA” deployed at community-based organizations (n=3) vs enhanced usual care (n=3) in different villages supported by the Maanasi program (enrolling approximately 60 women).

**Specific aim 3:** Throughout the duration of the funding period we will arrange for mentored participation of Psychiatry and Community Medicine residents from India in the research project. Community Health workers will benefit from regular videoconference didactic and case presentation (ECHO) sessions such as symptoms of and treatment for common mental disorders.

The grant will accomplish the goals of developing a unique mobile application that is scalable, examining its feasibility and building research capacity at the research site in India.

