Randomized trial: We will randomize CBOs to use MITHRA (n=3) or enhanced usual care (EUC) (n=3) for 12 weeks. Randomization will be clustered to account for distance from the PHC. The MITHRA CBOs will each have 2 -3 tablets for use by all attendees. A CHW will be present at meetings and encourage women to use the MITHRA app. During their time at the meeting, women will complete the PHQ-9 screening and modules based on their individual depression score. Privacy will be ensured. They will also have the option to take turns checking out the tablet for viewing at home (if this is reported by the design group to be a desirable feature). In the EUC CBOs, CHWs will offer monthly group education (45 min) regarding the symptoms of depression, informed by training webinars led by study Investigators. We have the support of the CBO and PHC leadership for this project (see attached letters of support). In both MITHRA and EUC CBOs CHWs will conduct community outreach to encourage women to attend meetings, as depression can lead to amotivation and women with depression may be less likely to attend CBO meetings. All CHWs will receive training in depression, screening and common treatments, resources and referrals.

**Outcome Measures:** CHWs will maintain rosters of CBO attendees at MITHRA CBOs and EUC CBOs. In monthly review sessions with the study investigators, the CHWs will review questionnaire completion and scores, and directly contact the woman (by phone or home visit or at a CBO meeting) if there is a need to step up care beyond that advised by the app. Women typically attend CBO meetings 2 -3 times a month and use at every attendance will be encouraged.

**MITHRA** is an app which will be available on 2 -3 tablets placed in Community Based Organizations (CBOs). Women can log in to MITHRA using a unique password protected secure single user sign on (fingerprint sign in to account for varying levels of literacy) to complete the physical health questionnaire and the PHQ -9 (validated Kannada version of the PHQ-9) in an assigned private place in the CBO. On completion of the PHQ-9, each woman will receive a prompt based on her total score (see Fig). Women who score < 5 will watch general information on depression; women who score 5 – 10 will watch modules 1 and 2 (case descriptions, What is Depression? and Introduction to PHQ-9) Women who score 10 – 15 will watch modules 1, 2, and 3 (Connection between activity and mood).

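### Whole CBOs are randomised, three per arm, but the single-visit arm comparisons treat about 60 women as independent

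*Combined protocol and SAP*

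**What the plan says.** Section 5.1 (Randomized trial) fixes the unit of allocation: "We will randomize CBOs to use MITHRA (n=3) or enhanced usual care (EUC) (n=3) for 12 weeks". Section 1.5, Specific Aim 2, places the CBOs "in different villages supported by the Maanasi program" and expects about 60 women in total. On how location enters the allocation, section 5.1 says only: "Randomization will be clustered to account for distance from the PHC". It does not say whether this means pairs, strata or something else.

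Delivery is also at CBO level. In the intervention arm: "The MITHRA CBOs will each have 2 -3 tablets for use by all attendees". In the control arm: "In the EUC CBOs, CHWs will offer monthly group education (45 min) regarding the symptoms of depression".

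The Statistical Methods section, the only statistical text in the document, sets out the between-arm analysis: "At each time of assessment, outcome parameters were compared between study groups using independent t test or Mann Whitney U test as appropriate". It adds that "RMANOVA was performed to compare the change in the outcome scores over time between study groups", and it uses a 0.05 significance level. Neither that section nor any other names a CBO effect, an ICC, a design effect, a robust standard error or a cluster-level analysis. Distance from the primary health center (PHC) is not used in the analysis either.

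**The concern.** The independent t test and the Mann-Whitney test both assume that women are independent within and between arms. Here women in the same CBO share a village, and they share either that CBO's tablets or its group education sessions, so their scores may be correlated. The protocol itself expects location to matter, since it brings distance into the randomisation.

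With positive within-CBO correlation, the t test on 58 df understates the standard error of an arm difference that rests on six randomised units. Chance differences between six villages could then be reported as an effect of the app on PHQ, QIDS, WHODAS or BADS.

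**Working it through.** **Inputs.**
- From the documents: 6 CBOs, 3 per arm; about 60 women; significance level 0.05; three assessments of the research depression score (baseline, 3 and 6 months, section 5.4).
- Assumed: a two-sided test; equal clusters with no loss, 60/6 = 10 women per CBO and 60 − 2 = 58 df; an ICC ρ of 0.01, 0.02, 0.05, 0.10 or 0.20.
- Also assumed: f, the share of between-CBO variance that is common to a pair matched on distance and so removed by pairing.

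The documents give no power or sample-size figure to reproduce.

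**Step 1: check without clustering.** At ρ = 0 the simulated type I error of the t test is 0.0498, as it should be.

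**Step 2: true against assumed variance.** In units of 2σ²/30, the true variance of the arm difference is 1 + 9ρ − 10ρf. The naive pooled estimate has expectation 1 − (9/29)ρ. At ρ = 0.10 and f = 0 these are 1.90 and 0.969, so the true standard error is √(1.90/0.969) = 1.40 times the assumed one. At f = 0.5 they are 1.40 and 0.969, a ratio of √(1.40/0.969) = 1.20.

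Break-even is where the two are equal: 10f = 9 + 9/29, so f = 0.93 whatever the ICC.

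**Step 3: type I error of the single-visit tests.** Null trials, at least 40,000 per cell:

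| Test and f | ρ=0.01 | 0.02 | 0.05 | 0.10 | 0.20 |
|---|---|---|---|---|---|
| t test, f=0 | 0.061 | 0.071 | 0.104 | 0.157 | 0.255 |
| t test, f=0.5 | 0.055 | 0.060 | 0.075 | 0.102 | 0.154 |
| t test, f=0.8 | 0.051 | 0.052 | 0.060 | 0.066 | 0.082 |
| t test, f=0.93 | 0.049 | 0.050 | 0.050 | 0.050 | 0.053 |
| t test, f=1 | 0.049 | 0.049 | 0.047 | 0.041 | 0.037 |
| Mann-Whitney, f=0 | 0.060 | 0.069 | 0.099 | 0.153 | 0.245 |
| Mann-Whitney, f=0.5 | 0.054 | 0.057 | 0.074 | 0.099 | 0.147 |

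A separate calculation of the f = 0 t-test row with 2,000,000 draws gave 0.060, 0.071, 0.104, 0.158 and 0.252.

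**Step 4: cluster size.** Section 1.8a describes groups of about 15 to 20 members. With 15 or 20 women per CBO, ρ = 0.05 and f = 0, the t-test error is 0.134 or 0.162 instead of 0.104.

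**Step 5: RMANOVA group-by-time test.** A CBO effect that is constant over visits cancels: the simulated error is 0.051 at ρ = 0.05 and 0.053 at ρ = 0.20. The test is affected only if CBOs differ in change over time. As an illustration, assume complete data at three visits, independent visit errors and an independent CBO-by-visit effect with the same ICC range. The error is then 0.064 / 0.080 / 0.127 / 0.214 / 0.359 at f = 0 and 0.058 / 0.063 / 0.086 / 0.126 / 0.207 at f = 0.5.

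**Step 6: does a CBO-level test work?** A t test on the six CBO means (4 df) has error 0.048 to 0.051 at f = 0. It falls from 0.047 to 0.027 across the ICC range at f = 0.5, and from 0.044 to 0.011 at f = 1. With baseline adjustment (regress follow-up on baseline ignoring arm, then average the residuals by CBO) the ranges are 0.049 to 0.052, 0.030 to 0.050 and 0.013 to 0.050. It holds the level or is conservative.

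A permutation test of the six CBOs could never reach p<0.05: the smallest two-sided p is 2/20 = 0.10, or 2/8 = 0.25 with three pairs.

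**Step 7: interval width.** The ratio to the naive width is √(1+9ρ) × 2.776/2.002: 1.45 at ρ = 0.01 and 2.32 at ρ = 0.20. A factor of 2.776/2.002 = 1.39 is the loss of df. Mean simulated ratios are slightly lower, 1.37 to 2.26.

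**The case against.** **It is an exploratory feasibility study.** Under Aim 2, "we will examine feasibility and utility of" the app. There is no stated efficacy hypothesis, primary outcome, power claim or decision rule tied to a between-arm p-value. This limits the harm, and the feasibility aim is untouched. But the Statistical Methods section does apply p<0.05 to arm comparisons of clinical scores, and section 1.7 ticks generalisable knowledge and leaves the pilot and feasibility box blank. If a threshold is used, the test has to match the design.

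**The size is not in the documents.** This stands. At an ICC of 0.01 to 0.02, or with 80% of the variance removed and an ICC up to 0.05, the error is 5% to 7%, which matters little in practice. The omission is certain and its consequence is not. That favours an analysis that is valid at any ICC over one that assumes zero.

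**Distance may already deal with it.** Only if it removes about 93% or more of the between-CBO variance. The documents do not say how distance was used, so that cannot be taken for granted.

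**Equal clusters of ten are an assumption.** True, but larger clusters make the inflation worse.

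**A mixed model is fragile with six CBOs.** In null trials the CBO variance is estimated as zero in about 53 / 49 / 38 / 25 / 11% of trials across the ICC range. Overall error stays at about 3% to 5%, so the model is not invalid. The reported ICC would often be uninformative, however, and the CBO-mean test is the safer choice.

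**Conclusion.** The concern holds. The single-visit between-arm tests ignore the unit of randomisation and over-reject whenever CBOs differ by more than the distance restriction removes. For an assumed ICC of 0.01 to 0.20 and ten women per CBO, the t test's true error at nominal 5% is about 6% to 25% with nothing removed, 5.5% to 15% with half removed, and 5% to 8% with 80% removed. There is no inflation at an ICC of zero or above the break-even of about 93%. The RMANOVA likewise has no CBO term, but its group-by-time test is affected only if CBOs differ in change over time.

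This must be fixed before any between-arm p-value on the clinical scores is relied on. The conclusion does not extend to the comparison of change scores, the baseline chi-square or Fisher tests, or the within-arm McNemar test.

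**What to change.** 1. State in one sentence how distance from the PHC entered the allocation.
2. Replace the individual-level between-arm tests with a t test on the six CBO means of baseline-adjusted QIDS-SR at 3 and at 6 months, on 4 df. This remains valid, if conservative, should the CBOs have been paired; a paired 2-df analysis is optional.
3. An acceptable alternative is a linear mixed model with random CBO and woman effects, a CBO-by-visit effect if all visits are modelled, and Satterthwaite or Kenward-Roger df. Expect frequent zero estimates of the CBO variance.
4. Treat any other score compared between arms in the same way.
5. Report the difference, its 95% CI and the ICC, and make no efficacy claim from an individual-level p<0.05.

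**Cost.** Revised SAP wording and a re-run on the same data; no new data are needed. The Statistical Methods section is written in the past tense, so in practice this means reanalysis and restrained reporting. Fewer results will be called significant, because intervals on 4 df are wider by the ratios in Step 7. With the optional paired analysis the ratio is √(1 + 9ρ − 10ρf) × 4.303/2.002: at an ICC of 0.20, about 2.9, 2.4 or 1.9 if pairing removes 50, 80 or 100%. Under fully effective pairing the unadjusted 4-df test is conservative, with error down to about 1% at an ICC of 0.20.

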## 4 RECRUITING and SCREENING PARTICIPANTS

**4.1 Recruiting and Screening.** Describe how subjects will be identified, recruited, and screened. Include information about: how, when, where, and in what setting. Identify who (by position or role, not name) will approach and recruit subjects, and who will screen them for eligibility.

End user focus group: Women for the end user focus group will be recruited from via i) advertisements ii) flyers iii) word of mouth and iv) community health workers (CHWs). We will oversample for women with depressive symptoms such that we have an equal number of women with Patient Health Questionnaire -9 (PHQ-9) score above 5 and PHQ-9 score below 5. [For prescreening](#), to identify women with a PHQ-9 above 5, [community health workers located in the Community Based Organization \(CBO\) will use the PHQ-9 questionnaire](#), introduced with talking points which have been [uploaded](#).

Provider focus group: Primary care and mental health providers will be recruited from Anekal Primary Health Center and CHWs will be recruited from the Community Based Organizations (CBOs) and by contacting them through the parent Mahila Mandal Organization.

All advertisements and flyers will be reviewed and approved before use by the Human Subjects division at University of Washington.

For the RCT, participants will be recruited from community-based organizations (CBOs) via i) advertisements ii) flyers iii) word of mouth and iv) community health workers (CHWs). Our recruitment strategies will enable us to recruit women with varying degrees of depression and to be representative of women in the villages covered by the CBO.

All advertisements and flyers will be reviewed and approved before use by the Human Subjects division at University of Washington.

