2. Depression measured by Quick Inventory of Depressive Symptoms (QIDS SR) at baseline 3 months and 6 months. QIDS SR will be collected by a blinded / masked research assistant. Research assessments will be conducted over the phone or in the Primary Health Center to avoid unblinding of CBO randomization status (presence of tablets in the CBOs)
3. Behavioral Activation – Behavioral Activation Depression Scale (BADS). We will administer the BADS to all women to calculate adherence to behavioral activation recommendations (for intervention women) and to measure degree of behavioral activation (for Enhanced Usual Care women).
4. Mental health services utilization – At baseline, 3 months and 6 months. We will obtain information on rates of utilization of mental health services including number of contacts with mental health providers and details of medications taken.

Depression – clinical outcome (not research measure)- Patient Health Questionnaire – 9. We will obtain information on rates of utilization of mental health services including the number of contacts with mental health providers and details of medications taken.

**5.5 Data sources.** For all types of data that will be accessed or collected for this research: Identify whether the data are being obtained from the subjects (or subjects' specimens) or whether they are being obtained from some other source (and identify the source).

*If you have already provided this information in Question 5.1, you do not need to repeat the information here.*

All research measures will be obtained from subjects by research coordinators in person or by phone.

**5.6 Identifiability of data and specimens.** Answer these questions carefully and completely. This will allow HSD to accurately determine the type of review that is required and the relevant compliance requirements. Review the following definitions before answering the questions:

**Access** means to view or perceive data, but not to possess or record it. See, in contrast, the definition of "obtain".

**Identifiable** means that the identity of an individual is or may be readily (1) ascertained by the researcher or any other member of the study team from specific data variables or from a combination of data variables, or (2) associated with the information.

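### No planned between-arm comparison uses the baseline score as a covariate, which usually gives up some precision with three CBOs against three

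*Combined protocol and SAP*

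**What the plan says.** The Statistical Methods section at the end of the combined document is the only analysis text. It has three between-arm comparisons of the outcome scores:

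- At each visit: "outcome parameters were compared between study groups using independent t test or Mann Whitney U test as appropriate".
- On change: "Change in the outcome at 3 and 6 months from baseline was compared between the study groups using Wilcoxon signed rank test".
- Over time: "RMANOVA was performed to compare the change in the outcome scores over time between study groups".

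It names no covariate and no ANCOVA, regression or mixed model. It does not say which comparison is the main one.

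The baseline value exists for the main depression scale. Section 5.4 lists "Depression measured by Quick Inventory of Depressive Symptoms (QIDS SR) at baseline 3 months and 6 months". For BADS, section 5.4 gives no visit times ("We will administer the BADS to all women to calculate adherence to behavioral activation recommendations"). PHQ-9 is listed there as a clinical outcome, also without visit times, and WHODAS is not listed at all.

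On design, section 5.1 says "We will randomize CBOs to use MITHRA (n=3) or enhanced usual care (EUC) (n=3) for 12 weeks" and "Randomization will be clustered to account for distance from the PHC". Section 1.5 gives about 60 women, and section 4.1 expects a wide spread at entry: "Our recruitment strategies will enable us to recruit women with varying degrees of depression".

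**The concern.** The visit-by-visit tests give baseline a slope of 0. A comparison of mean change gives it a slope of 1, and so does any contrast of follow-up with baseline in a group-by-time term. The slope that the data support is rho × SD(follow-up)/SD(baseline), which usually lies between the two. Which fixed slope does less harm depends on rho and the SD ratio, and neither is known in advance. An estimated slope is usually close to or better than the better of the two, and it avoids the larger loss from the worse one.

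Two things are at stake. One is the width of the interval, in a trial with six randomised units. The other is the estimate when the arms happen to differ at baseline: the raw and change estimates then differ by exactly the baseline difference, and the plan does not say which to believe.

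One separate fault bears on this. The signed rank test named for the change comparison is a paired test and does not compare two independent arms. The working below takes the intended comparison to be one of mean change between arms.

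**Working it through.** The plan states no power, SD, ICC or correlation, so there is no figure of its own to reproduce.

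**Inputs from the documents.** Three CBOs against three (section 5.1). About 60 women (section 1.5), hence 10 per CBO and 30 per arm if sizes are equal. QIDS-SR at three visits (section 5.4).

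**Assumptions, not in the documents.** ICC 0.05 (range 0.01–0.10); rho 0.3, 0.5 or 0.7; SD ratio (follow-up/baseline) 1 (range 0.8–1.25); CBO-level correlation equal to rho (alternatives 0 and 0.9); unmatched randomisation; no dropout; comparison of means, not ranks. Units are baseline SDs.

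**Step 1: closed form, slope taken as known.**
SE(raw) = sqrt{(2/3) × [ICC + (1 − ICC)/10]} = sqrt{(2/3) × (0.05 + 0.095)} = 0.311.
The change score multiplies the variance by 2(1 − rho). Adjustment multiplies it by 1 − rho². At rho 0.5 the factors are 1.00 and 0.75, so the SEs are 0.311 and 0.269.

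**Step 2: simulation with the slope estimated.** There were 40,000 trials per setting. The adjusted analysis takes the pooled within-arm slope and then runs a t test on six adjusted CBO means. Raw and change scores are also tested on CBO means.

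| rho | SE raw | SE change | SE adjusted | Gain over better | Gain over worse |
|---|---|---|---|---|---|
| 0.3 | 0.310 | 0.369 | 0.299 | 4% | 19% |
| 0.5 | 0.310 | 0.310 | 0.271 | 13% | 13% |
| 0.7 | 0.312 | 0.241 | 0.225 | 7% | 28% |

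The closed form for the adjusted SE is 0.297, 0.269 and 0.222, within 0.003 of the simulation. Type I error of the adjusted test with 4 df was 5.1–5.8% over all settings in step 3.

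**Step 3: wider assumptions.** With rho 0.3, 0.5 and 0.7, the gain over the better comparison is 4%, 5% and 0% at SD ratio 1.25, and 4%, 12% and 20% at SD ratio 0.8. Over all 81 combinations of ICC, rho, CBO-level correlation and SD ratio, the gain runs from +21% to −4%. In 15 of the 81 there is no gain or a small loss, nearly all at ICC 0.10 with CBO-level correlation 0, or at SD ratio 1.25. Worst case: SE 0.315 for change against 0.328 adjusted (0.328/0.315 = 1.04), at ICC 0.10, rho 0.5, CBO-level correlation 0.9, ratio 1.25.

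**Step 4: chance baseline imbalance.** The SD of the baseline difference between arms is sqrt(2/30 × 1.45) = 0.311, so P(|difference| > 0.3 SD) is about 34% at ICC 0.05.

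Given a +0.3 SD difference, let b_C be the slope of CBO-mean follow-up on CBO-mean baseline, and b the pooled within-arm slope. The mean estimates shift by 0.3 × b_C (raw), 0.3 × (b_C − 1) (change) and 0.3 × (b_C − b) (adjusted). With ratio R and CBO-level correlation rho_C:

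- c = ICC × rho_C + (1 − ICC) × rho/10, and v = ICC + (1 − ICC)/10
- b_C = R × c/v
- b ≈ R × [54(1 − ICC) × rho + 40c]/[54(1 − ICC) + 40v], from 54 df within CBOs and 4 df between CBOs in an arm (4 × 10 = 40)

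Three cases:

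- **rho_C = rho = 0.5, R = 1:** b_C = b = 0.5. Shifts +0.15 / −0.15 / 0.00.
- **ICC 0.10, rho 0.7, rho_C = 0, R = 1:** b_C = 0.063/0.19 = 0.332; b ≈ (34.02 + 2.52)/(48.6 + 7.6) = 0.650. Shifts about +0.10 / −0.20 / −0.10.
- **ICC 0.10, rho 0.5, rho_C = 0.9, R = 1.25:** b_C = 1.25 × 0.135/0.19 = 0.888; b ≈ 1.25 × (24.3 + 5.4)/56.2 = 0.661. Shifts about +0.27 / −0.03 / +0.07.

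Adjustment therefore removes the imbalance exactly only when the woman-level and CBO-level relations agree. In the third case it leaves more than the change score does.

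**Step 5: what it buys.** Power for a 0.5 SD effect with a 4-df test on CBO means, raw/change/adjusted, at ICC 0.05: 24/18/27% (rho 0.3), 24/24/31% (rho 0.5), 24/36/42% (rho 0.7). The plan does not include such a test. Baseline adjustment that ignores CBO has type I error of about 10% at ICC 0.05 and rho 0.5.

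**The case against.** The strongest case against is that baseline is already used. The change comparison and the repeated-measures ANOVA both involve it, and against the better of raw and change the gain under the central assumptions is only 4–13%. None of the governing quantities is in the documents, and some plausible values give no gain. Aim 2 concerns feasibility and utility, so no firm conclusion should turn on a narrower interval. The analysis also has a larger fault, unmodelled clustering, which this change does not cure. Finally, the methods are written in the past tense, so the change may amount to a re-analysis.

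These points limit the size of the benefit but do not remove it. Using baseline with a fixed slope of 1 is not the same as estimating the slope, and the plan does not choose between the raw and change comparisons. A feasibility trial that reports between-arm tests at p < 0.05 is still better served by a tighter, clearly designated estimate.

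A reader might infer three stronger points that the documents do not support:

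- **That the plan ignores baseline, or that its estimates are biased.** Baseline enters through change and the ANOVA. Under randomisation the raw and change mean comparisons are both unbiased over repetitions.
- **That adjustment always gains precision and fully cancels a chance imbalance.** Steps 3 and 4 show otherwise.
- **That the ANOVA tests a group main effect in which baseline is part of the outcome.** The text says that it compares change over time between groups, which most naturally means the group-by-time term.

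**Conclusion.** The concern holds as a matter of efficiency. No planned comparison conditions on the baseline score, although QIDS-SR at baseline is scheduled, and this usually gives up some precision. Under the central assumptions (six CBOs of 10, ICC 0.05, equal SDs, the same correlation at both levels) the SE falls by about 4–13% against the better planned comparison and 13–28% against the worse. At rho 0.5 the closed-form 95% half-width with 4 df falls from 2.776 × 0.311 = 0.86 to 2.776 × 0.269 = 0.75 SD. Over the wider grid the range is +21% to −4%.

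Protection against chance imbalance is real but partial unless the woman-level and CBO-level relations agree. The trial remains low-powered with or without adjustment. The figures apply to mean comparisons and not to the rank tests. The change should be made, but it ranks below the repair of the unmodelled clustering.

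**What to change.** For QIDS-SR, make the main between-arm estimate at 3 and at 6 months the follow-up score adjusted for each woman's own baseline score, within an analysis that accounts for CBO and is valid with six clusters. For example: regress follow-up on arm and baseline, subtract slope × baseline from each woman's score, and run a t test on the six adjusted CBO means. Report the raw and change comparisons as secondary.

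First state what the sentence in section 5.1 on distance from the PHC means. The test has 4 df if randomisation was unmatched and fewer if it was stratified or matched (2 df for three matched pairs).

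Use the woman-level baseline and not a covariate on CBO means. The latter spends a df and raises the critical value from 2.776 to 3.182, which under equal SDs cancels the gain over the raw comparison unless the correlation exceeds about 0.49.

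Extend the adjustment to BADS, WHODAS and PHQ-9 only where a baseline value is confirmed.

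Cost: no new QIDS-SR data, a few sentences of SAP text, a little more analysis work, and a possible SE loss of up to about 4% in unfavourable settings. If results are already known, label it a re-analysis. This refines the repair of the clustering and does not replace it.
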